6 prerequisite for receiving the TeGeCoach intervention; participants can elect their preferred physician
7 prior to program start, or are alternatively referred to an already contracted physician by their health
8 coach. To encourage physicians to participate, they enter into an integrated care contract with the
9 respective health insurance fund that provides financial incentives for the delivery of special medical
10 services throughout the intervention.⁶⁷ The enrolment and reimbursement of contracted physicians is
11 coordinated by medicalnetworks (Kassel, Germany), a company that is specialized on the management
12 of integrated care programs (ICPs) within the § 140a volume V of the German Social Security Code (SGB
13 V). If the physician of choice refuses to participate, the participant is referred to a nearby contracted
14 physician that has already entered into the integrated care contract. Once enrolled, the health coach
15 contacts the contracted physician to discuss their tasks during the course of the study. Due to
16 recruitment barriers, it is possible that no suitable physician can be found for the patient by the end of
17 the recruitment phase. For safety reasons, participants for whom no physician can be appointed do not
18 receive TeGeCoach.

19

20 **Treatment allocation and blinding**

21 Participants are allocated in a 1:1 ratio to either the TeGeCoach or CAU group, stratified by health
22 coaching center using a permuted block method within each stratum. In order to prevent selection bias
23 and to eliminate any predictability (allocation concealment), participants are randomly allocated via
24 Sealed Envelope (London, United Kingdom), a secure internet-based randomization service including
25 concealment, stratification and blocking for each health coaching site.

26 Blinding of care providers (health coaches and contracted physicians) and participants is not possible
27 because of obvious differences between the TeGeCoach intervention and CAU. However, as supported
28 by the CONSORT guidelines, blinding of the analysis is achieved by engaging an independent data analyst
29 and by withholding information about how the groups were coded before analytical decisions have been
30 completed.⁶⁸

31

32 **Interventions**

33 *TeGeCoach*

34 TeGeCoach is a 12-month long structured HEP that is designed to inspire healthy habits in patients
35 with PAD based on the transtheoretical model of behavior change. The main strategies used to improve

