25 exercise plan, checks if any contraindications to exercise exist, and whether all important comorbidities
26 such as high blood pressure, diabetes and coronary heart disease are sufficiently treated. Furthermore,
27 they receive three health reports from the health coach during the course of the program, which are
28 important for the joint exchange of information to provide collaborative care.

29 *Telephone health coaching:* Over the course of 12 months, patients regularly receive health
30 information leaflets and have up to nine structured 30-60 minute phone calls with their health coach.
31 During these structured phone calls, the health coach and the patient jointly discuss the progress
32 towards exercise goals and review the activity tracker data to check whether the patient adheres to the
33 walking plan. For this purpose, exercise sessions (i.e. intermittent walking represented as changes
34 between walking and break intervals) are visualized and automatically identified as an exercise session
35 by the health coaching platform. Additional phone calls are warranted when no data has been received,

1 no steps were taken or when coaches are alerted that the amount of exercise days has fallen below an
2 individual threshold. During these calls, barriers like lack of motivation, exercise intolerance or technical
3 issues are discussed and how they can be overcome through behavioral support. Along with the walking
4 exercise, patient-tailored topics of interest that are relevant to the management of PAD are discussed
5 in order to improve health literacy, to facilitate patient empowerment and to adopt a proactive stance
6 in dealing with their disease. The health coaching curriculum includes: Knowledge of PAD, PAD
7 medication, comorbidities of PAD and other related health topics (e.g. tobacco use, nutrition). The
8 health coaches use an electronic documentation system to monitor the coaching process (*KKH*
9 *Kaufmännische Krankenkasse* and *mhplus Krankenkasse*: Picama® Managed Care, Trustner GmbH; *TK*
10 *Techniker Krankenkasse*: Philips GmbH Market DACH). The telephone health coaching is carried out by
11 three health coaching centers that are located throughout Germany, each affiliated to one of the three
12 statutory health insurance funds (Health Coaching Center of *KKH Kaufmännische Krankenkasse*,
13 Telemedical Center at Robert-Bosch-Hospital on behalf of *TK Techniker Krankenkasse*, Health Coaching

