 12 ⁸²⁻⁸⁴; nicotine dependence (FTND) ⁸⁵; health literacy (HLQ) ^{86 87}; patient activation (PAM-13
 13 questionnaire) ^{88 89}
- 14 - *Claims data: Total health care costs, i.e. inpatient hospital care costs; outpatient (ambulatory)*
 15 *services and primary care costs, costs for drugs and other medical supplies, sick pay costs;*
 16 *healthcare resource use, i.e. time period until hospitalization, probability of hospitalization,*
 17 *number and duration of inpatient hospitalization, outpatient medical treatment, drug dose*
 18 *(defined daily dose, DDD); (severe) adverse events, i.e. death, amputation, and*
 19 *revascularization (see supplementary file)*

20

21 *Additional outcomes (intervention arm only)*

- 22 - *PROM: Patient satisfaction (ZAPA questionnaire)* ⁹⁰
- 23 - *Activity tracker data: Exercise adherence, e.g. number of alerts and corresponding phone calls*
 24 *made when step frequency or the duration of exercise sessions fall below an individual*
 25 *threshold range; amount of steps/net walking time (>50 steps/minute) per day/week*

26

27

28 **Table 2.** Participant timeline: Time schedule of enrolment (eligibility screen, informed consent, pseudonymization and
 29 allocation), study arms (TeGeCoach or CAU) and measurements (questionnaires and claims data).

	Study period			
	Enrollment	Allocation	Postallocation	
Time point *1	-t1	t0	t1	t2
Enrollment				
Eligibility screening (claims data)	x			
Informed consent	x			
Pseudonymization		x		
Allocation		x		
Study arms				
TeGeCoach (intervention)		◆	◆	◆
CAU (control)		---	---	▶
Measurements				

Intervention and control arm				
PROMs (questionnaires) *2		X	x	x
Cost and medical outcomes (claims data) *3		◆	◆	◆
Intervention arm only				
ZAPA questionnaire			x	
Walking exercise parameters (activity tracker data) *4		◆	◆	

- 1
- 2 *1 -t1: ~1 month before patient in, t0: baseline; t1: 12 month follow-up t2: 24 month follow-up
- 3 *2 WIQ, EQ5D-5L, SF-12, VascuQoL-25, PHQ-9, GHD-7, AUDIT-C, FTND, HLQ, PAM-13
- 4 *3 Health care costs, healthcare resource use, (severe) adverse events
- 5 *4 Exercise adherence, amount of steps/net walking time (>50 steps/minute) per day/week

6

7 **Sample size**

8 To find a ‘meaningful’ effect that is clinically relevant, practicable and economically feasible, the

9 sample size is calculated based on the distribution-based minimal clinically relevant difference (MCID)

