4 Claims data are routinely collected for the purpose of billing and contains information on all contacts
5 with the health care system including ICD codes, operations and procedure key (OPS) codes (the German
6 equivalent to the American procedure coding system, PCS), medication prescriptions and amount of sick
7 leaves. After study completion, the health insurance funds assemble and pseudonymize the claims data
8 and send it to the study team (University Medical Center Hamburg-Eppendorf). No individual insurance
9 information can be identified from this data.

10 Activity tracker data are automatically uploaded to the electronic documentation system via SIM card
11 modem (econnect, IEM GmbH) once per day. The statutory health insurance funds share the activity
12 tracker data with the study team in pseudonymized form.

13 All data are stored for a maximum of 10 years, securely locked in cabinets and saved on password-
14 protected computers in areas with restricted access. Personally identifiable information of participants
15 and pseudonymization keys are only accessible to the data coordinators at each health insurance fund.
16 The pseudonymization keys are deleted two years after study completion so that virtually from this point
17 all data is fully anonymized. Regarding dissemination, all publicly available data are fully anonymized
18 and do not disclose identities. Participants have the right to be informed about their data. If a participant
19 decides to withdraw from the trial prematurely, the data already collected may be used, unless revoking
20 their informed consent. Deletion of the data cannot be requested if the data has already been
21 anonymized.

22

23 **Statistical analysis**

24 Analyses are by intention-to-treat in accordance with the CONSORT guidelines, i.e. participants who
25 do not adhere to or withdraw from the prescribed TeGeCoach intervention and for whom no doctor
26 could be appointed (see *recruitment* section) are included in the analyses as randomized. For
27 questionnaire data, changes from baseline to follow-up measurements are compared between study
28 arms using linear mixed models.⁹⁴ Single imputation using the Expected-Maximization algorithm are
29 applied for item-level missing data. Scale-level imputation of missing data is not necessary since this is
30 fully handled by estimating mixed models with full information maximum likelihood (FIML).^{95 96} In order

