31 to take correlation between the observations into account, models are adjusted for participant and
32 health coaching center characteristics. For claims data, changes over time between groups are
33 compared between study arms using random-effects regression models (difference-in-differences
34 method) after eliminating differences in observable baseline characteristics between groups with the
35 use of entropy balancing⁹⁷. Entropy balancing allows a better balancing compared to conventional

1 processes such as propensity matching. Tests of treatment effects are conducted at a two-sided
2 significance level of 0.05. In order to check the robustness of the results, subgroup analyses are
3 performed to determine the influence of baseline characteristics (e.g. degree of walking impairment),
4 health insurance fund (i.e. *KKH Kaufmännische Krankenkasse*, *TK Techniker Krankenkasse*, *mhplus*
5 *Krankenkasse*) and type of analysis (i.e. intention-to-treat and per-protocol).

6

7 **Data monitoring and harms**

8 This trial is not monitored by a data monitoring committee, and no interim analyses are performed
9 as TeGeCoach is a low risk, non-invasive intervention with no identifiable risks. Over the course of the
10 intervention, participants allocated to TeGeCoach are medically monitored by their treating physician
11 while having regular access to the usual care of PAD. The risks from the use of wearable activity trackers
12 is low; all devices have been certified and conform to health, safety, and environmental protection
13 standards for products sold within the European Union (CE certificate).

14

15 **Ethics and Dissemination**

16 The study protocol, the informed consent forms and all other documents that are handed out to the
17 participants have been reviewed and approved by the ethical review bodies (Medical Association
18 Hamburg; reference number: PV5708). The ethics committee will be informed in case of any
19 amendments made to the study protocol or informed consent forms.

20 Findings are disseminated widely through peer-reviewed manuscripts published in scientific journals,
21 reports to the funding body, international conference presentations and media press releases.
22 Furthermore, the study team realizes the value of open science and feels committed to information
23 exchange through data being accessible to the research community. Therefore, in an attempt to tackle

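### In the main text the only designated safety outcome is death, amputation and revascularisation; non-fatal exercise-related harms are neither pre-specified nor actively collected

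*Combined protocol and SAP*

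**What the plan says.** - **Harm outcome.** Under Outcome Measures, Secondary Outcomes, the claims-data entry reads "severe) adverse events, i.e. death, amputation, and" and continues "revascularization (see supplementary file". The list is introduced by *i.e.*; the same section uses *e.g.* when it gives examples, as for exercise adherence.
- **Other claims outcomes in both arms.** The same entry lists "healthcare resource use, i.e. time period until hospitalization, probability of hospitalization", then number and duration of inpatient stays, and outpatient treatment. No cause is stated, and the class is resource use, not safety.
- **Risk statement.** Data monitoring and harms gives up a monitoring committee and interim analyses "as TeGeCoach is a low risk, non-invasive intervention with no identifiable risks". That section names no harm to be collected.
- **Precautions elsewhere.** Under Recruitment, Physicians: "For safety reasons, participants for whom no physician can be appointed do not" receive TeGeCoach. Under Interventions, the contracted physician reviews the "exercise plan, checks if any contraindications to exercise exist, and whether all important comorbidities" are adequately treated.
- **Data held.** Data collection and management says claims cover all contacts "with the health care system including ICD codes, operations and procedure key (OPS) codes". On timing: "After study completion, the health insurance funds assemble and pseudonymize the claims data" and pass them to the study team.

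**The concern.** The intervention asks patients aged up to 80 to walk briskly to the limit of tolerable claudication pain, on at least five days a week. The harms one would want to compare between arms include non-fatal cardiac events, stroke, acute heart failure, and falls with injury or fracture. None is named as an outcome. In the text shown, nobody is asked to report such events to the trial.

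Two of the three listed components are hard to read as harm. Amputation belongs to the course of the disease. Revascularisation appears in the Introduction among the treatments for claudication, so its rate also reflects treatment choice. A difference in either could be benefit, harm or a change in referral.

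At stake is the low-risk premise. The authors foresee wide integration into usual care if TeGeCoach is effective. Followed as written, the trial would report a harm result that cannot separate non-fatal exercise-related events from disease course, treatment choice or all-cause hospital use.

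**Working it through.** **Step 1. Where could a non-fatal exercise-related event appear?**

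| Place in the plan | Arms | Can it identify the event? |
|---|---|---|
| Adverse events: death, amputation, revascularisation | both | no; no non-fatal cardiac, stroke or injury event is listed |
| Hospitalisation measures | both | only mixed with all other admissions |
| Outpatient treatment | both | no cause stated; the Recruitment section calls outpatient coding error-prone |
| Coach calls about exercise intolerance | TeGeCoach only | handled as a coaching barrier, not as an outcome |
| Medical monitoring by the physician | TeGeCoach only | no stated route of report to the trial |

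**Step 2. The risk statement beside the precautions.** One section says there are no identifiable risks. Two others withhold the programme on safety grounds when no physician is found, and require a check for contraindications to exercise. Low risk after screening is consistent with those rules; no identifiable risk is not.

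**Step 3. What would a specific outcome add?** The plan has no safety calculation to reproduce. Its primary sample size does reproduce: f = 0.15 is d = 0.30 for two groups, and 2 × (1.96 + 0.84)² / 0.30² gives 175 per arm by normal approximation (176 with the t-test). 880 × 0.20 = 176 and 880 × 0.30 = 264, as stated. This has no bearing on harm, except that claims do not depend on questionnaire return, so I take 880 per arm.

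Formula (two proportions, two-sided 5%, n = 880 per arm, p̄ the mean of p1 and p2):

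power = Φ[(|p2 − p1| − 1.96·SE0) / SE1], with SE0 = √(2·p̄(1 − p̄)/n) and SE1 = √([p1(1 − p1) + p2(1 − p2)]/n).

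Worked case, 3% v 1%: SE0 = √(2 × 0.02 × 0.98/880) = 0.00667; SE1 = √((0.0099 + 0.0291)/880) = 0.00666; (0.02 − 1.96 × 0.00667)/0.00666 = 1.04; power 0.85. Expected events are 26.4 v 8.8.

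All rates below are assumptions; the documents give none.

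| Specific outcome | Power |
|---|---|
| 1% v 0.5% | 0.23 |
| 1.5% v 1% | 0.15 |
| 2% v 1% | 0.41 |
| 3% v 2% | 0.27 |
| 4% v 3% | 0.21 |
| 4% v 2% | 0.69 |
| 3% v 1% | 0.85 |
| 8% v 5% | 0.72 |
| 6% v 3% | 0.86 |

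| The same 2-point excess inside all-cause hospitalisation | Power |
|---|---|
| 22% v 20% | 0.18 |
| 32% v 30% | 0.15 |
| 42% v 40% | 0.13 |
| 52% v 50% | 0.13 |

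A 2-point excess thus has power 0.69 (4% v 2%) or 0.85 (3% v 1%) as a specific outcome, and 0.13 to 0.18 when diluted. A fall in PAD admissions would mask it further, by an amount that the documents do not let one estimate.

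**The case against.** The strongest reply is that the plan is not blind to harm. All-cause death, the gravest harm, is counted. An excess of amputations or revascularisations would be a limb signal. Hospitalisation is measured in both arms. A screened and medically supervised walking programme can fairly be called low risk. All of this stands, and it limits what may be concluded. A reader might go further in several ways that the documents do not support:

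- **That the list is closed.** The sentence points to a supplementary file that is not shown. The limit can be asserted only for the main text.
- **That the components are end-stage events, or cannot show harm.** Revascularisation is also ordinary treatment for claudication, and an excess of limb events could reflect harm. They cannot show it cleanly.
- **That this is the trial's whole safety evidence.** It is the only outcome designated as safety; hospitalisation adds indirect evidence.
- **That the heart-failure exclusion (NYHA III/IV) shows recognised exercise risk.** The plan justifies it by inability to carry out the intervention and competing risks, not safety.
- **That fewer revascularisations would be presented as better safety.** Nothing in the text says so.

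The power figures are also open to challenge. Three-point excesses look favourable, while one-point excesses on a 1% to 3% base have power of only 0.21 to 0.41. Each event type alone would be rarer than a pooled outcome. Claims record diagnoses, not attribution to exercise. These are limits on the remedy; they do not supply the missing outcome.

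**Conclusion.** The point holds for the main text. The only designated safety outcome is three events, two of which are confounded with disease course and treatment choice, and non-fatal exercise-related harms are neither pre-specified nor actively collected. If the supplementary file adds such events, the main-text definition should be changed to match it.

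The gain from a specific outcome depends on rates that the documents do not give. Over the assumed range, power runs from about 0.15 to 0.86. These figures assume that claims are available for all 880 per arm, and they ignore the planned entropy balancing. Intention-to-treat keeps patients who never receive TeGeCoach in its arm, which would dilute any excess. A null result would not prove safety; the case rests on interpretable reporting by arm, not on a powered test.

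The mismatch between the risk statement and the precautions is one of wording. It does not show that the programme is unsafe, or that the decision against a monitoring committee was wrong. This is a change that should be made; it does not affect the primary analysis.

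**What to change.** 1. Before group codes are released, fix inpatient ICD code sets for non-fatal acute cardiac events, stroke, acute heart failure, and fall-related injury or fracture. Inpatient codes are preferable because the plan itself distrusts outpatient coding.
2. Report these by arm at 12 and 24 months, pooled and by type, as descriptive comparisons with confidence intervals.
3. Report amputation and revascularisation separately as limb outcomes, and death on its own.
4. Reconcile the no-identifiable-risks statement in Data monitoring and harms with the physician rule under Recruitment and the contraindication check under Interventions.
5. State in the main text what the supplementary file adds, if anything.

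**Cost.** Extra code lists on a claims extract that the funds already deliver for both arms; no patient contact. There will be a few more descriptive comparisons. The fix cannot attribute an event to exercise, misses injuries treated only as outpatients, and gives no ongoing monitoring, because claims arrive after study completion.

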10 for small changes on the WIQ following three months of a structured HEP that have been determined in

11 previous studies (WIQ speed MCID: 6%; WIQ distance MCID: 5%; WIQ stair climbing MCID: 5%).⁹¹ As

12 TeGeCoach is more intensive and longer, a small-to-moderate group difference was estimated (f=0.15),

13 while accounting for the inherited heterogeneity of this pragmatic trial that could lead to a dilution of

14 the treatment effect. Assuming a response rate of 30% (TeGeCoach) and 20% (CAU) from baseline 24-

15 month follow-up (t2)^{43 92}, a sample size of 1760 (880 per group) is required to have 176 and 264

16 participants at t2 in the CAU and intervention arm, respectively, which is sufficient to detect the

17 estimated small-to-moderate effect with 80% power and a 5% level of significance (Gpower v.3.1.9.2).

18

19 **Data collection and management**

20 Data management and storage are carried out in compliance with the General Data Protection

21 Regulation (GDPR) in the European Union and Good Scientific Practice guidelines by the German

22 Research Foundation.⁹³ To ensure confidentiality, all data are collected, processed, analyzed and stored

23 in de-identified form by replacing personally identifying information of each participant with a unique

24 patient identification number (i.e. by pseudonymization), which allows to combine data from multiple

25 sources and to merge longitudinal data. Linkage to an identity (depseudonymization) is not possible

26 without a separately stored pseudonymization key, which is protected by technical and organizational

27 measures.

28 At each study point, the data coordinators of the health insurance funds send out a set of paper-

29 based questionnaires (PROMs) to the participants. Participants are asked to send them back to the

30 Department of Medical Psychology at the University Medical Center Hamburg-Eppendorf. To maximize

31 response rates, participants who have not send their questionnaire back in time receive a postal

32 reminder after 2-4 weeks. All participants are followed up at t1 and t2, irrespective of whether

33 questionnaires have been returned at previous study points. Questionnaire data are entered into an

1 electronic database, with only authorized personnel being allowed to retrieve, enter or change data. For
2 data quality and monitoring purposes, validation checks regarding out of range data, illogical and invalid
3 responses and data entry errors are performed.

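### Is the stated 80% power wrong for the 176 and 264 responders expected at 24 months?

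*Combined protocol and SAP*

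**What the plan says.** The Sample size section gives all the inputs. The effect is set in the clause "TeGeCoach is more intensive and longer, a small-to-moderate group difference was estimated (f=0.15", that is, a Cohen's f of 0.15. Retention is set by "Assuming a response rate of 30% (TeGeCoach) and 20% (CAU) from baseline 24" months after baseline. The section then states that "a sample size of 1760 (880 per group) is required to have 176 and 264" "participants at t2 in the CAU and intervention arm, respectively, which is sufficient to detect the" "estimated small-to-moderate effect with 80% power and a 5% level of significance (Gpower v.3.1.9.2"). It cites the software but not the test that was run in it.

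Three facts from other sections matter. Under Treatment allocation and blinding, "Participants are allocated in a 1:1 ratio to either the TeGeCoach or CAU group". Under Statistical analysis, "Tests of treatment effects are conducted at a two-sided" level of 0.05. The same section says how the primary outcome will be analysed: for "questionnaire data, changes from baseline to follow-up measurements are compared between study" arms with linear mixed models.

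**The concern.** The section attaches 80% power to a pair of unequal counts, 176 and 264. A reader who enters those counts and f = 0.15 into a two-group test gets clearly more than 80%, and a reader who works back from 80% power at the stated response rates gets fewer than 1,760 participants. Either way the printed figures seem not to fit together.

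A power statement that cannot be reproduced can mean that the wrong effect size, error rate or number of participants was used. If the mismatch ran the other way, the trial would be short of participants for its own target effect. Even in this direction, the text would give a wrong idea of how much further non-response the design could absorb, in a trial that already plans for 70% to 80% non-response.

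**Working it through.** **Inputs.** f = 0.15, 80% power, response 20% (usual care) and 30% (TeGeCoach), and 880 per arm, all from Sample size. 1:1 allocation from Treatment allocation and blinding. Two-sided 5% from Statistical analysis.

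**Assumption.** The calculation was a two-group comparison of 24-month responders. With equal arms, f = 0.15 is a difference of d = 2 × 0.15 = 0.30 SD.

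**Step 1: the plan's counts.** 880 × 0.20 = 176 and 880 × 0.30 = 264. Both match.

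**Step 2: the plan's total.** Power comes from the noncentral t distribution with noncentrality d × √(n₁n₂/(n₁+n₂)).

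- 175 per arm: 0.30 × √87.5 = 2.806, power 79.9%.
- 176 per arm: 0.30 × √88 = 2.814, power 80.1%.

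So 176 is the smallest equal arm that reaches 80%. Then 176/0.20 = 880 per arm and 2 × 880 = 1,760. The stated total is reproduced exactly if both arms are sized on the lower response rate.

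**Step 3: power at the expected counts.** n₁n₂/(n₁+n₂) = 176 × 264/440 = 105.6, which equals the information in 211.2 per arm with equal arms.

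- Holding d = 0.30: 0.30 × √105.6 = 3.083, power 86.8%.
- Holding f = 0.15 with a 40:60 split: d = 0.15/√(0.4 × 0.6) = 0.306, power 88.1%. Entering N = 440 in the two-group F test gives the same value.

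**Step 4: enrolment needed for exactly 80% at both stated response rates.** With m per arm, the counts are 0.2m and 0.3m, so n₁n₂/(n₁+n₂) = 0.06m²/0.5m = 0.12m. Power of 80% at d = 0.30 is reached at m = 730.6, or about 731 per arm and 1,462 in total. The plan has 880 − 731 = 149 more per arm.

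**Step 5: other tests that could have been run.** An F test with two numerator degrees of freedom at N = 440 and f = 0.15 gives 80.8%. A two-sided 2.5% level with 176 and 264 at d = 0.30 gives 79.7%. The documents state neither. The exact fit in Step 2 makes the balanced two-group test the likelier source, but does not prove it.

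**The case for a change.** The best case for a change rests on the word *required*. On the two-group reading, 1,760 is not required at the stated response rates: about 1,462 would do. The larger number follows only from a step that the text leaves out, and a protocol should let its sample size be recomputed without guessing. The test is also unnamed. And because such heavy non-response is expected, readers have a fair interest in knowing how far response could fall before power drops below 80%.

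Part of this stands. The wording is looser than it could be, and one clause naming the test and saying that the lower-response arm set the size would have spared the reader the reconstruction. But the step can be recovered from the printed 20%, 176, 880 and 1:1 ratio, and sizing on the worse arm is ordinary caution.

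The argument about tolerance for non-response is weaker. Any such margin would describe a comparison of complete 24-month responders, whereas the plan uses a mixed model fitted by full-information maximum likelihood to all available measurements. The power of that model cannot be computed from the documents. Nor would any such figure address bias from non-response, which is a separate matter.

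**Conclusion.** The concern does not call for a change. Every printed count reproduces, and saying that 176 and 264 are sufficient for 80% power is an at-least statement, which 86.8% (d = 0.30) or 88.1% (f = 0.15) satisfies. The gap of about 7 to 8 points is in the safe direction: on this reading the trial is not underpowered for its target effect.

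These figures assume a two-group, two-sided 5% test at 24 months, which the documents do not name. On the two-degree-of-freedom alternative, the printed 80% would be close to exact. What remains is an unstated but conservative sizing step. Writing it down would alter no enrolment, analysis or conclusion: recruitment is listed as completed in the trial registration table (Table 1), and a restated 87% would describe a test other than the one planned.
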